### 9.2.5.1. Follow-up Visit

Patients will undergo follow-up to collect results of biological and genetic tests if there is cardiac fixation on a radionuclide bone scintigraphy and/or SPECT.

## 9.3. Variables

Variable	Data source(s)
Patient informed consent date	PATIENT INCLUSION
Patient visit date	PATIENT INCLUSION
Age ≥50 years	PATIENT INCLUSION
LVH Echo demonstrated end-diastolic LV MWT ≥15mm	PATIENT INCLUSION
Maximal end diastolic wall thickness	PATIENT INCLUSION
Sarcomeric HCM (Genetic testing)	PATIENT INCLUSION
Plasma cell dyscrasia	PATIENT INCLUSION
Fabry disease	PATIENT INCLUSION
AL, AA or any other amyloidosis	PATIENT INCLUSION
Severe aortic stenosis (defined as) Maximal aortic velocity >4 m/s or Mean gradient >40 mmHg	PATIENT INCLUSION
Birth date (mm-yyyy)	PATIENT INFORMATION
Gender	PATIENT INFORMATION
Weight	PATIENT INFORMATION
Height	PATIENT INFORMATION
Ethnic Origin	PATIENT INFORMATION
Date	CLINICAL EVALUATION
Diastolic blood pressure	CLINICAL EVALUATION
Systolic blood pressure	CLINICAL EVALUATION
Diagnosed hypertension	CLINICAL EVALUATION
Antihypertensive medication	CLINICAL EVALUATION
Coronary artery disease	CLINICAL EVALUATION
Renal insufficiency	CLINICAL EVALUATION
Diabetes Mellitus	CLINICAL EVALUATION
Lumbar spinal stenosis 1	CLINICAL EVALUATION
CTS – surgery history 2	CLINICAL EVALUATION
New York heart Association (NYHA) class	CLINICAL EVALUATION
Atrial Fibrillation (AF)	CLINICAL EVALUATION

Variable	Data source(s)
Pacemaker	CLINICAL EVALUATION
AICD (Automatic Implantable Cardiac Defibrillator)	CLINICAL EVALUATION
LGE (Late Gadolinium Enhancement)	CLINICAL EVALUATION
Heart rate	CLINICAL EVALUATION
Sinus rhythm	CLINICAL EVALUATION
PR Interval	CLINICAL EVALUATION
QRS interval	CLINICAL EVALUATION
Sokolow index	CLINICAL EVALUATION
Pseudo-MI pattern	CLINICAL EVALUATION
Poor precordial R wave progression	CLINICAL EVALUATION
LBBB RBBB Paced Intraventricular conduct delay	CLINICAL EVALUATION
Left Ventricular Ejection Fraction (LVEF)	CLINICAL EVALUATION
Left Ventricular Obstruction Tract (LVOT)	CLINICAL EVALUATION
Longitudinal strain done?	CLINICAL EVALUATION
LV end-diastolic diameter	CLINICAL EVALUATION
MWT	CLINICAL EVALUATION
MWT at septum	CLINICAL EVALUATION
MWT posterior wall	CLINICAL EVALUATION
Hypertrophic pattern Apical, Concentric, Asymmetric, Mix	CLINICAL EVALUATION
LV mass index	CLINICAL EVALUATION
Aortic valvular stenosis	CLINICAL EVALUATION
Pericardial effusion	CLINICAL EVALUATION
Patient scintigraphy date	SCINTIGRAPHY
99mTc-DPD, 99mTc-PYP, 99mTc-HMDP	SCINTIGRAPHY
Grade 0=absent cardiac uptake Grade 1=mild uptake less than bone Grade 2=moderate uptake equal to bone Grade 3=high uptake greater than bone	SCINTIGRAPHY
Walking ability: No Impairment, Impaired but ability to walk without a stick or crutches, Walking only with the help of one stick or crutch, Walking with the help of two sticks or crutches, Confined to a wheelchair or bedridden	ATTR RED FLAGS
SPECT date	SPECT
SPECT Result	SPECT
Paresthesia / Numbness / Sensory loss *	ATTR RED FLAGS
Pain*	ATTR RED FLAGS
Temperature sensory loss*	ATTR RED FLAGS
Muscle weakness*	ATTR RED FLAGS
Carpal tunnel syndrome symptoms	ATTR RED FLAGS
Erectile dysfunction / Vaginal dryness	ATTR RED FLAGS
Orthostatic / postural hypotension (dizziness, syncope)	ATTR RED FLAGS
Urinary difficulties (i.e. dysuria, incontinence...)	ATTR RED FLAGS
Sweating abnormalities	ATTR RED FLAGS
Digestive dysautonomia: Constipation, alternating constipation and diarrhoea, nausea, vomiting...	ATTR RED FLAGS
Early satiety / Gastro paresis	ATTR RED FLAGS
Unintentional weight loss	ATTR RED FLAGS
Visual disturbances: Dry eye / Glaucoma	ATTR RED FLAGS
Creatinine	CLINICAL LABORATORIES
Haemoglobin	CLINICAL LABORATORIES

Variable	Data source(s)
BNP	CLINICAL LABORATORIES
NTproBNP	CLINICAL LABORATORIES
Troponin I	CLINICAL LABORATORIES
Troponin T	CLINICAL LABORATORIES
IFE of serum	CLINICAL LABORATORIES
IFE of urine	CLINICAL LABORATORIES
*sFLC assay	CLINICAL LABORATORIES
Electrophoresis performed?	CLINICAL LABORATORIES
Date	TTR gene sequencing
Result	TTR gene sequencing

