### 2. Exclusion Criteria:

- a. Etiological diagnosis explaining the LVH prior to patient inclusion (eg, Sarcomeric HCM, Myeloma, Fabry disease, Sarcoidosis, any type of amyloidosis [AA, AL, TTR])
- b. Severe aortic stenosis defined as aortic valve area (AVA)  $< 1.0$  cm^2

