## 2. Exclusion Criteria:

- a. Etiological diagnosis explaining the LVH prior to patient inclusion (eg, Sarcomeric HCM, Myeloma, Fabry disease, Sarcoidosis, any type of amyloidosis [AA, AL, TTR\*\*]).
- b. Severe aortic stenosis defined as aortic valve area (AVA) <1.0 cm^2.

*\*\* TTR diagnosis at exclusion criteria: Direct relative (siblings or parents) of a carrier with a known hereditary mutation in the TTR gene or any patient already diagnosed by any of the following: cardiac fixation at the bone scintigraphy, TR mutation at the genetic testing, biopsy with amyloidosis (positive red congo) and positive TTR staining.*

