## 5 ANALYSIS SETS/POPULATIONS

### 5.1 FULL ANALYSIS SET

#### **Full Analysis Set 1 – Primary population**

Full Analysis Set 1 (FAS1) includes all patients who meet eligibility (inclusion/exclusion) criteria and with a radionuclide bone scintigraphy and/or SPECT performed with 99mTc-DPD/99mTc-PYP/99mTc-HMDP.

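### The eligibility variable for severe aortic stenosis uses velocity or gradient, while the exclusion criterion that defines FAS1 uses valve area

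*Protocol*

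**What the plan says.** Protocol 9.2.5 gives the second exclusion as "Severe aortic stenosis defined as aortic valve area (AVA) <1.0" (in cm²). The Protocol abstract and SAP 2.1 state the same criterion. None of the three mentions velocity or gradient.

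The variable table in Protocol 9.3, with patient inclusion as the data source, describes the same exclusion as "Severe aortic stenosis (defined as) Maximal aortic velocity >4 m/s or Mean gradient >40 mmHg". It does not mention valve area.

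SAP 5.1 says that FAS1 "includes all patients who meet eligibility (inclusion/exclusion) criteria" and also requires a scan with one of the three tracers. SAP 8.2 assigns the primary endpoint to FAS1. Neither document says which definition of severe aortic stenosis prevails, or how to classify a patient on whom the two disagree.

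**The concern.** Valve area, peak velocity and mean gradient are separate measurements. The two definitions can therefore disagree in either direction:

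- **Area below 1.0 cm², velocity and gradient at or below their limits.** The 9.3 variable does not flag this patient, but the written criterion excludes the patient. The risk is wrongful inclusion in FAS1.
- **Area 1.0 cm² or more, velocity or gradient above its limit.** The 9.3 variable flags this patient, but the written criterion does not exclude the patient. If the flag was acted on, the patient never entered the dataset.

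Both errors affect the denominator of the primary result. Protocol section 7 names aortic stenosis among the conditions that often coexist at the older ages at which wild-type ATTR presents. Discordant patients therefore cannot be assumed to have average scan positivity. Any resulting error would be a bias, which the confidence interval does not cover.

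**Working it through.** **1. The passages side by side**

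| Place | Measure used for severe aortic stenosis |
|---|---|
| Protocol abstract, exclusion b | Valve area < 1.0 cm² |
| Protocol 9.2.5, exclusion b | Valve area < 1.0 cm² |
| SAP 2.1, exclusion b | Valve area < 1.0 cm² |
| Protocol 9.3, patient-inclusion variable | Velocity > 4 m/s or mean gradient > 40 mmHg |

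All of this is current text. The three statements of the criterion agree, and the 9.3 row is the exception.

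**2. Can the criterion be checked from other data?** In part. SAP 6.3 (cardiological manifestations) uses aortic valve area, maximal velocity and mean gradient as e-CRF items, and Protocol 9.3 lists aortic valvular stenosis under clinical evaluation. Valve area therefore appears to be collected. However, Protocol 9.1 collects assessments only if they were performed, and SAP 7 imputes nothing. A patient with no recorded valve area cannot be shown to meet or to fail the criterion, and no rule covers that case.

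**3. The plan's own precision.** Protocol 9.5 assumes a prevalence of 10%, N = 1500 and a two-sided 95% interval:

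1.96 × √(0.10 × 0.90 / 1500) = 0.0152, or ±1.52 points. This reproduces the stated ±1.5.

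**4. Possible shift in the primary prevalence.** Let d be the share of discordant patients and q the scan positivity among them, with 10% positivity in everyone else. Keeping the discordant patients rather than removing them changes the estimate by

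shift = [0.10 × (1 − d) + q × d] − 0.10 = d × (q − 0.10).

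The documents give neither d nor q, so both are assumptions. The 10% is the planning figure, which Protocol 9.5 states for ATTR-CM; it is used here as a stand-in for scan positivity.

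| d | Patients of 1500 | Shift at q = 0% | Shift at q = 30% | Half-width if removed |
|---|---|---|---|---|
| 1% | 15 | −0.1 | +0.2 | 1.53 (n = 1485) |
| 3% | 45 | −0.3 | +0.6 | 1.54 (n = 1455) |
| 5% | 75 | −0.5 | +1.0 | 1.56 (n = 1425) |
| 10% | 150 | −1.0 | +2.0 | 1.60 (n = 1350) |

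Shifts and half-widths are in percentage points. For example, with d = 5% and q = 30%, 0.10 × 0.95 + 0.30 × 0.05 = 0.110, a shift of +1.0. At q = 10% there is no shift at any d.

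The loss of precision is negligible. Within this grid the shift exceeds 1.5 points only at 10% discordance, and then only if positivity among the discordant patients is far above 10%.

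**The case against.** The strongest reply is that the FAS1 rule is not ambiguous. SAP 2.1 sets out the criteria itself, agrees with the Protocol abstract and 9.2.5, and SAP 5.1 refers to those criteria. One row in a variable table does not amend them. This stands: a reader might infer that FAS1 membership is undefined or depends on the choice between two rules, but as written it is area-based. What remains is that the variable listed for checking the exclusion does not measure it.

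A reader might also infer that sites screened on velocity and gradient. The documents do not show this. The CRF is a stand-alone appendix that is not part of them, and Protocol 9.2.2 says that patients meeting the inclusion and exclusion criteria are invited. Wrongful screening is therefore a possibility, not a finding.

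A third tempting step is to extend the point to "Plasma cell dyscrasia", which 9.3 lists where the criterion names myeloma. That does not hold. The criterion reads "Etiological diagnosis explaining the LVH prior to patient inclusion (eg, Sarcomeric HCM, Myeloma, Fabry disease, Sarcoidosis, any type of amyloidosis", and its list consists of examples only. A broader capture field does not contradict an open list, and nothing says that a recorded dyscrasia excludes a patient by itself.

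Finally, the size rests wholly on assumed inputs, and even the extreme corner of the 1–5% range stays below the planned precision. That is fair, and it limits the severity.

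**Conclusion.** Wrong as written: an internal inconsistency of low to moderate severity. The exclusion is defined by valve area in three places and by velocity or gradient in the variable meant to record it, and no rule covers discordant patients or a missing valve area.

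The effect on the primary prevalence cannot be derived from the documents. It is about −0.5 to +1.0 point if 1–5% of patients are discordant and 0–30% of them are scan-positive, with 10% positivity in the rest. It is zero if discordant patients have the same positivity as the others. The conclusion that the passages conflict does not depend on these assumptions; only the size does.

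**What to change.** 1. Reconcile the Protocol abstract, Protocol 9.2.5, Protocol 9.3 and SAP 2.1 to one definition of severe aortic stenosis. Which one is a clinical decision on which this review takes no position.
2. State in SAP 5.1 that FAS1 eligibility on this criterion is derived from the recorded echocardiographic values under the reconciled definition, and how a patient is classified when the needed measurement is missing.
3. Report the number of enrolled patients whom the two definitions classify differently, with the primary prevalence and its 95% interval under each as a sensitivity row.
4. Check the non-inclusion register (Protocol 9.2.2) for patients turned away on this criterion. It is the only route to patients already screened out, since they are not in the analysis data.

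The cost is a text clarification, one derivation rule and one added table row. Data collection was planned to end in June 2022 (Protocol section 6) and SAP version 2 is dated 06-Jul-2022, so on that schedule a CRF change would come too late to alter screening. Items 2 and 3 remain feasible wherever the measurements were recorded.

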#### 9.4. Data sources

Data will be collected from medical records and routine clinical practice. As an epidemiological study, there are no specific requirements with regard to patient procedures to be performed or the treatment regimen. Data from each patient will be reported on an electronic case report form (e-CRF).

An electronic Case Report Form (e-CRF – Appendix 3) will be used for data recording. In this protocol, the term e-CRF should be understood to refer to medical records in electronic data form. The data collection method used will be an e-CRF for physicians in English.

The visit after scintigraphy/SPECT should be documented only when the bone scintigraphy is positive with tracer uptake (Grade 1, 2 or 3) or SPECT shows cardiac fixation.

It is the investigator's responsibility to ensure completion and to review and approve all e-CRFs. E-CRFs must be signed by the investigator or by an authorized staff member. These signatures serve to attest that the information contained on the e-CRFs is true. Anytime, the investigator has the final personal responsibility for the accuracy and authenticity of all clinical and laboratory data entered into the e-CRF.

#### 9.5. Study Size

Considering a prevalence of ATTR-CM around 10%, the screening of N =1500 patients will provide a precision of  $\pm 1.5\%$  in the estimation of this prevalence with a 95% two-sided confidence interval (first objective). In addition, considering such a prevalence, the precision of the estimation of the different symptoms or additional signs within the population of ATTR-CM (other objectives) will be estimated with a precision of  $\pm 7.3\%$  for any sign/symptom with a frequency of 30% or lower.

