## Study size

The study is designed to enroll approximately 1500 patients.

Considering a prevalence of ATTR-CM around 10%, the screening of 1.500 patients will provide a precision of  $\pm 1.5\%$  in the estimation of this prevalence with a 95% two-sided confidence interval (primary objective). In addition, considering such a prevalence, the prevalence of the different symptoms or additional signs within the population of ATTR-CM (other objectives) will be estimated with a precision of  $\pm 7.3\%$  for any sign/symptom with a frequency of 30% or lower.

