## Milestones

The study will enroll approximately 1500 patients.

Milestone	Planned date
Start of data collection	September 2017
End of data collection	June 2022 or as soon as 1000 patient will be screened in the study

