## 5. AMENDMENTS AND UPDATES

Amendment number	Date	Protocol section(s) changed	Summary of amendment(s)	Reason
N°1	14 JUN 2018			New European legislation
N°2	11 FEBRUARY 2020	Inclusion/ Exclusion criteria Variables CRF ICD Milestone	Clarification of the protocol process to be in line with the requirement of a NIS protocol Addition of the SPECT in the inclusion criteria Inclusion period extension	Protocol clarification and deletion of the biological sample collection
N°2.1	22 OCTOBER 2020	Milestone	Extension for the data collection	Due to the international pandemic and to allow to reach the goal of the number of patient screened, it was decided to extend the inclusion period
N°2.2	21 MAY 2021	Milestone	Extension for the inclusion period and data collection	Due to the international pandemic and to allow to reach the goal of a minimum of one thousand patient screened, it was decided to extend the inclusion period. Participating country list updates
N°2.3	04 NOVEMBER 2021	Milestone	Extension for the inclusion period and data collection	Due to the international pandemic and to allow to reach the goal of a minimum of one thousand patient screened, it was decided to extend the inclusion period.

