## 6. MILESTONES

Milestone	Planned date
Feasibility meeting	06 – 07 October 2017
Start of data collection	May 2018
End of data collection	June 2022
Final study report	December 2022

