**Figure 2. Study Flow Chart**

**9. RESEARCH METHODS**

## 9.1. Study Design

TTRACK is an epidemiological multicenter and multinational study.

Patients can be enrolled from several countries listed in Appendix 5. This list is non-exhaustive and additional countries may be added to this list.

The management of this protocol will be aligned with country legislation and regulatory procedures.

Investigators will be cardiologists experienced in diagnosis of cardiomyopathies or physicians specialized in diagnosing patients with LVH. The sites involved (at least when performing feasibility) will be representative of their respective country in terms of practice. Participating physicians will not be influenced in their decision making and routine proceedings in any way.

The study will include approximately 1500 patients.

All assessments described in this protocol are performed as part of routine clinical practice or standard practice guidelines for the patient population and healthcare provider specialty in the countries where this non-interventional study is being conducted. Data, including individual study results, will be collected from these assessments, if performed.

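### The stated precision (±1.5 and ±7.3 points) assumes 1500 patients and ATTR-CM, but data collection may end at 1000 and the primary endpoint is grade 1–3 cardiac fixation

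*Protocol*

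**What the plan says.** **Size and precision.** Protocol 9.5 states: "Considering a prevalence of ATTR-CM around 10%, the screening of N =1500 patients will provide a precision of" ±1.5%. It then gives ±7.3% for signs or symptoms of 30% frequency or lower within ATTR-CM. The abstract (Study size) repeats both figures and says "The study is designed to enroll approximately 1500 patients". Protocol 9.1 agrees: "The study will include approximately 1500 patients".

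**End of collection.** The abstract's Milestones open with "The study will enroll approximately 1500 patients", but the end of data collection is given as "June 2022 or as soon as 1000 patient will be screened in the study". In Protocol 6 the row "End of data collection" carries June 2022 alone, with no patient count.

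**Endpoint.** The abstract ties the ±1.5% for ATTR-CM to the main aim: "in the estimation of this prevalence with a 95% two-sided confidence interval (primary objective"; section 9.5 calls it the first objective. Protocol 8 sets the primary objective on cardiac fixation, and SAP 6.3 defines fixation as grade 1, 2 or 3. SAP 6.3 reserves ATTR amyloidosis for grade 2 or 3 without monoclonal protein abnormalities.

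**The concern.** The study tests no hypothesis (SAP 4.1) and has no power calculation, so the width of the confidence interval is the whole case for its size. That width is given for one scenario, and other current text departs from the scenario in two ways.

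- **Number of patients.** The abstract's milestones permit an end at two thirds of the number on which the precision rests. A reader cannot tell whether 1000 is a floor or a stop.
- **Quantity estimated.** The figure offered for the primary objective is computed for ATTR-CM, a subset of the patients who meet the primary endpoint. The primary endpoint itself has no stated precision.

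At stake is whether the plan promises a precision that its own end rule need not deliver. The validity of the estimates is not in question.

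**Working it through.** **Inputs.** From Protocol 9.5: two-sided 95% interval, ATTR-CM prevalence 10%, N = 1500, sign frequency 30%. From the abstract's Milestones: N = 1000. The documents give no fixation prevalence, so 15% and 20% are assumptions.

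**Formula.** Half-width = 1.96 × √(p(1 − p)/n).

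**Step 1: reproduce the plan's figures.**
- Prevalence: 1.96 × √(0.10 × 0.90/1500) = 1.52 points, stated as 1.5.
- Sign: 10% of 1500 is 150 cases; 1.96 × √(0.30 × 0.70/150) = 7.33 points, stated as 7.3.

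Both are correct for their inputs.

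**Step 2: same inputs at 1000 patients.**
- Prevalence: 1.96 × √(0.10 × 0.90/1000) = 1.86 points, a loss of 0.34.
- Sign: 10% of 1000 is 100 cases; 1.96 × √(0.30 × 0.70/100) = 8.98 points.
- Ratio to 1500: √(1500/1000) = 1.22, so both are 22% wider.

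At 1000, a half-width that rounds to 1.5 needs a prevalence of about 6.7% or less.

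**Step 3: the primary endpoint.** Fixation comprises SAP-defined ATTR, grade 2–3 with a monoclonal protein, and grade 1. Its prevalence is therefore at least that of ATTR, and below 50% a higher prevalence widens the interval at fixed n. The last two columns use the Wilson score method planned in SAP 8.1.

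| Fixation prevalence | Half-width, n = 1500 | Half-width, n = 1000 | Wilson 95%, n = 1500 | Wilson 95%, n = 1000 |
|---|---|---|---|---|
| 10% (the plan's ATTR-CM figure) | 1.52 | 1.86 | 8.58–11.62 | 8.29–12.02 |
| 15% (assumed) | 1.81 | 2.21 | 13.28–16.90 | 12.92–17.35 |
| 20% (assumed) | 2.02 | 2.48 | 18.05–22.10 | 17.64–22.59 |

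**Step 4: what n means.** FAS1 requires eligibility and a scan actually performed (SAP 5.1), while the inclusion criteria admit patients who only plan one. Red-flag data are recorded if available (Protocol 9.2.2), missing values are not imputed (SAP 7), and percentages refer to filled data (SAP 8.1). The n above is therefore evaluable FAS1 patients, or cases with data, not patients screened.

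**The case against.** **1000 may simply be a minimum.** The reason given for amendment 2.3 is to "reach the goal of a minimum of one thousand patient screened", which supports a target of 1500 with a floor of 1000. That reading is reasonable. But the current milestone words 1000 as an end point, and no precision is stated for it on either reading.

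**The calendar date can end the study short as well.** This is correct. June 2022 appears in both milestone tables, so deleting the 1000 clause would not secure 1500 patients.

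**The ATTR-CM wording is loose, not wrong.** Protocol 7 and SAP 2 both call ATTR-CM prevalence the main purpose. The exclusion footnote in Protocol 9.2.5 counts cardiac fixation among the ways of being already diagnosed with TTR. The interim trigger of 75 grade 1–3 patients (Protocol 9.7) is half of 150, which is consistent with an expectation of about 10% fixation. On that view ±1.5 already describes fixation, and at 1500 it survives rounding up to a prevalence of about 10.5%. This explains the wording and limits how much can be made of it. It does not put a precision for the declared primary endpoint on paper.

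**The signs objective.** A reader might infer that ±7.3 is also unsupported because Protocol 8 sets the signs objective in fixation-positive patients. The documents do not bear that out at 1500. Fixation-positive patients are at least as numerous as ATTR-CM patients, so the figure is conservative for them, and SAP 8.2 reports signs in FAS3.1 (ATTR), where it applies directly. Only the fall to 100 ATTR-CM cases at N = 1000 matters.

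**Conclusion.** The point holds and is minor. The stated precision is arithmetically sound but tied to 1500 patients. If collection ends at 1000, the same inputs give ±1.9 and ±9.0 points instead of ±1.5 and ±7.3. That result needs no outside assumption.

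The endpoint mismatch is real in the sizing paragraphs, but its size depends on an unknown fixation prevalence: nothing if fixation is 10%, and 1.8–2.0 points at 1500 if it is 15–20%.

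Two stronger readings should be resisted. One is that the target has been cut to 1000 or that the study will stop there: three places in the current text still say about 1500, and the milestone can be read as a floor. The other is that the primary endpoint is in doubt or its estimate biased: Protocol 8 and SAP 6.3 define it clearly, the analysis is mainly descriptive (SAP 4.2), and the Wilson intervals will use the n achieved.

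**What to change.** 1. Reconcile 1500 and 1000 across the abstract (Study size, Milestones) and Protocol 6, 9.1 and 9.5. Say whether 1000 is a minimum or a stopping point, and how it relates to the June 2022 date.
2. In the abstract and 9.5, restate the primary precision for grade 1–3 cardiac fixation at 1500 / 1000 evaluable FAS1 patients: 10%, ±1.5 / 1.9 points; 15%, ±1.8 / 2.2; 20%, ±2.0 / 2.5. Mark the fixation prevalence as an assumption.
3. State the precision for a 30% sign within ATTR-CM, at 10% ATTR-CM prevalence, as ±7.3 points with 150 cases with data and ±9.0 with 100.
4. If the ATTR-CM prevalence figure is kept, describe it as ATTR prevalence in FAS1, matching the SAP 8.2 table. Do not relabel it as the protocol's secondary objective, whose denominator is patients with cardiac fixation.

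**Cost.** This is wording in five places. The analysis and the Wilson interval are unchanged, and stating both sizes requires no extra patients. The price is a slightly less favourable stated precision. If the sponsor instead makes 1500 binding, that is more than wording: it could mean up to 500 further patients or a later end date.
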